Mitochondrial Stress, Brain Imaging, and Epigenetics (MiSBIE)

Statistical Analysis Plan

NCT04831424

October 6, 2023

Outcome Measures

Primary Outcome Measure:

1. *Average TSST-induced elevation in cortisol*

This is designed to measure cortisol reactivity to the trier social stress test (TSST), quantified from salivary cortisol (LC-MS) over an 8-timepoints timecourse. The elevation will be measured as the area under the curve (AUC) for the cortisol time course.

[Time Frame: Day 1 post challenge (approximately 2 hours)]

SAP and Results: The AUC analysis for salivary cortisol reactivity to the TSST utilized two metrics: AUCg, where the ground is set at zero, and AUCi, where the ground is set at the baseline level. Given the non-Gaussian distribution of both groups, we applied the Mann-Whitney U test to compare the Control and MitoD groups. For AUCg, the MitoD group's cortisol level was 31.9% higher than the Control (64.49 ng/mL vs. 48.97 ng/mL), but this difference was not statistically significant ($p = 0.40$). The AUCi showed a significant 86.8% higher level in the MitoD group compared to the Control (20.91 ng/mL vs. 11.21 ng/mL, $p = 0.049$).

2. *Average allostatic load index*

Groups will be compared on a quantitative allostatic load (AL) index integrating baseline fasting measures of neuroendocrine, immune and metabolic systems, urinary catecholamines, hematological measures, and hair/diurnal cortisol levels.

[Time Frame: Blood collected on Day 1]

SAP and Results: We calculated allostatic load using the standard count-based index (Juster et al., 2024). In short, for each biomarker, we calculated the 12.5th, 25th, 75th, and 87.5th percentile according to sex-specific reference ranges. We used these percentiles to score each variable as either dysregulated (1) or not dysregulated (0) and summed each variable's score to produce the final allostatic load value. Using the non-parametric Mann-Whitney test, we find that allostatic load is significantly higher in participants with mitochondrial disease than in controls ($p = 0.018$), with a medium effect size (Hedge's $g = 0.52$).

Secondary Outcome Measures:

3. *Average TSST-induced elevation in heart rate*

Groups will be compared on heart rate (HR) as a measure of cardiovascular reactivity to stress, monitored using a continuous 3-lead ECG. The elevation will be computed from the baseline HR to the peak HR reached during the TSST.

[Time Frame: Day 1 post challenge (approximately 2 hours)]

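### The primary cortisol outcome is defined as one AUC but tested as two, AUCg (p = 0.40) and AUCi (p = 0.049), with no deciding metric, alpha, sidedness or multiplicity rule, so the unqualified claim of significance for AUCi is not supported

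*SAP*

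**What the plan says.** SAP, Primary Outcome Measure 1, is titled "Average TSST-induced elevation in cortisol". Its definition names one summary measure without saying which type: "The elevation will be measured as the area under the curve (AUC) for the cortisol time course".

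The results paragraph under the same item uses two: "The AUC analysis for salivary cortisol reactivity to the TSST utilized two metrics: AUCg, where the ground is set at zero, and AUCi", the latter referenced to the baseline level. Control and MitoD are compared by Mann-Whitney U.

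- **AUCg:** the MitoD "cortisol level was 31.9% higher than the Control (64.49 ng/mL vs. 48.97 ng/mL"), "but this difference was not statistically significant", p = 0.40.
- **AUCi:** "The AUCi showed a significant 86.8% higher level in the MitoD group compared to the Control", 20.91 against 11.21, p = 0.049.

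Primary Outcome Measure 2, the allostatic load index, is also called significantly higher in mitochondrial disease (p = 0.018). Its components include "hematological measures, and hair/diurnal cortisol levels".

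Neither the protocol nor the SAP, as provided, gives a significance level, the sidedness of the tests, which AUC decides, how the two primary outcomes combine, or an adjustment for multiple tests. Aim 1 in the protocol speaks of stress reactivity and names no AUC type.

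**The concern.** One primary outcome has been tested twice without adjustment, the two tests disagree, and the conclusion is taken from the one that falls 0.001 below an unstated threshold. The 0.05 level itself has to be inferred from 0.049 being called significant.

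Whether the cortisol outcome is positive therefore depends on a rule that the text does not record. If AUCg decides, p is 0.40. If both metrics count, AUCi needs adjustment. If AUCi alone was fixed in advance, 0.049 may stand. The plan and the findings are merged under one SAP and Results label, in the past tense, so the document cannot show which of these applied before the data were seen. The choice of family also affects how the second primary outcome can be reported.

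**Working it through.** **Inputs.** From the SAP, Primary Outcome Measures 1 and 2: p = 0.40 (AUCg), 0.049 (AUCi), 0.018 (allostatic load, AL). Assumed, because the documents do not say: alpha 0.05, two-sided tests, and the correlation r between the AUCg and AUCi test statistics, shown over a range. The Mann-Whitney p-values cannot be reproduced without participant data, so they are taken as printed.

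**1. Both cortisol metrics counted equally.** Holm and Bonferroni both multiply the smaller p by 2: AUCi = 2 × 0.049 = 0.098. Holm leaves AUCg at 0.40.

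**2. Allowing for correlation.** With bivariate normal statistics, the adjusted AUCi p is 1 − P(|Z1| < 1.969 and |Z2| < 1.969), where 1.969 is the two-sided normal value for 0.049. The chance of at least one false positive uses 1.960 instead. The last column is the raw p at which the adjusted value would equal 0.05.

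| r (assumed) | Adjusted p, AUCi | Chance of at least one false positive | Raw p needed |
|---|---|---|---|
| 0 | 0.096 | 9.75% | 0.025 |
| 0.5 | 0.089 | 9.1% | 0.027 |
| 0.7 | 0.082 | 8.4% | 0.029 |
| 0.9 | 0.069 | 7.0% | 0.035 |

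At r = 0.99 the adjusted p is still above 0.05 (about 0.055). Read as one-sided, the values at r = 0.5, 0.7 and 0.9 are 0.086, 0.079 and 0.067, so sidedness does not change the answer.

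**3. AUCi as the sole cortisol metric, with AL.** Holm: AL = 2 × 0.018 = 0.036 and AUCi = 1 × 0.049 = 0.049, so both pass. Plain Bonferroni gives AUCi 0.098.

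**4. All three tests in one family.** Holm: AL = 3 × 0.018 = 0.054, AUCi = 2 × 0.049 = 0.098, AUCg = 0.40. None passes. A correlation-aware (minimum-p) value for AL, from simulated trivariate normal statistics, runs from 0.053 to 0.042 over assumed AUCg–AUCi correlations of 0 to 0.9 and AL–AUC correlations of 0 to 0.4. Independence of AL is not assumed, because the index contains cortisol measures.

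**5. Percentages (separate).**
- 64.49/48.97 − 1 = 31.69%. With each input moved by half a unit in its last digit the range is 31.67% to 31.72%. Printed: 31.9%.
- 20.91/11.21 − 1 = 86.53%, range 86.40% to 86.66%. Printed: 86.8%.

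Rounding of the inputs explains neither. The group values are printed in ng/mL, a concentration, whereas an area under a time course has concentration × time units.

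**The case against.** The best defence is that the text already points to AUCi. The outcome is an elevation, and AUCi is the only one of the two metrics measured from baseline. The parallel secondary outcome for heart rate uses the same TSST-induced elevation wording and computes it from baseline to peak. Aim 1 also separates chronic from reactive biomarkers. This is good evidence and it stands as far as it goes: AUCi is the better-matched metric. It is still not a rule. The heart-rate item states its baseline reference and the cortisol item does not, while AUCg is analysed first under the same outcome and is never called supportive.

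A second defence is that both metrics and both raw p-values, including the null AUCg result, are printed, in a study that describes itself as beginning to explore mechanisms. That is fair, and it limits the remedy to a correction of wording and reporting.

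Two stronger readings are tempting, and the documents support neither. A reader might infer that AUCi was picked after seeing the results. The text does not show that; it only fails to show the reverse. A reader might also infer that AUCi fails under any proper multiplicity rule. It does not. It keeps 0.049 if it was fixed in advance as the sole cortisol metric and tested unadjusted or with allostatic load by Holm. It also does so if a fixed order or gatekeeping rule set in advance put it ahead of AUCg.

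**Conclusion.** The point holds as a correction to a stated conclusion. Two unadjusted tests were run on one primary outcome, with a chance of about 7.0% to 9.75% of at least one false positive at correlations from 0.9 down to 0, and significance was claimed from one of them without a recorded rule. With both metrics counted equally, AUCi does not reach 0.05 at any correlation examined. With a documented prior choice of AUCi, the claim can survive.

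Allostatic load is secure when the family is the two primary outcomes (0.036). It is marginal when all three tests count: 0.054 by Holm, on either side of 0.05 when correlation is allowed for.

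These results rest on an assumed two-sided alpha of 0.05, the printed p-values, and correlations that the documents do not give. The percentage mismatch is a minor, separate erratum with no bearing on the significance question.

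**What to change.** State the alpha, the sidedness and the members of the primary family in the SAP. Then search for a dated record of the metric choice.

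- **If a record shows AUCi was chosen in advance:** name it the primary cortisol metric with AUCg supportive, and report Holm-adjusted values over AUCi and allostatic load (0.049 and 0.036) beside the raw ones.
- **If no record exists:** report Holm over all three tests (AUCg 0.40, AUCi 0.098, allostatic load 0.054). Describe the cortisol result as suggestive, say that any labelling of AUCi as primary was made after the results, and note that allostatic load is then marginal.

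As a separate erratum, check the four group values at source, correct either the values or the percentages (the printed values give 31.7% and 86.5%), and print AUC in concentration × time units.

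The cost is wording, a few adjusted p-values, a record search and a check of four numbers. No new data are needed. The downside, if no record is found, is less favourable primary conclusions.

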perform “repeat” visits on two healthy volunteers. This will provide essential quantitative information on some novel mitochondrial parameters that are measured in the MiSBIE study (cell bioenergetics, cell-free mitochondrial DNA, metabolic markers), including how they may vary within a person over time, relative to between- person differences. These difficult to obtain data can be used to quantify intra- individual variation over months-to-years and provide an empirical basis to evaluate the magnitude of differences among the primary study outcomes between the MiSBIE study groups.

Description of Subject Population

Sample #1

Sample subject population:

Subject Population	Number of completers required to accomplish study aims	Projected number of subjects who will be enrolled to obtain required number of completers	Age range of subject population
Individuals with the m.3243A>G mitochondrial DNA mutation	30	33 (accounting for 10% attrition or unusable data)	18 to 60

Description of subject population:

We will investigate individuals carrying the m.3243A>G tRNA^{Leu(UUR)} mutation which is the most frequent mtDNA point mutation, and presents in the most severe case as MELAS (Mitochondrial Encephalopathy, Lactic Acidosis, and Stroke-like episodes) (50, 51) as well as non-MELAS carrier relatives. From this cohort and the existing patient registry, individuals who have previously had genetic diagnostic testing confirming the presence of the m.3243A>G will be identified and invited to participate in the study. Maternally related individuals with a first-degree relative who is a known carrier of the mutation are considered “obligate carriers” and will also be included.

Individuals without a confirmed genetic test who are otherwise eligible and who have family members with 3243A>G mitochondrial DNA mutation and/or suspect they have the mutation will be invited to provide a buccal or urine sample to test for mitochondrial mutations. The genetic counselor or physician will review the specific consent form for genetic testing

Protocol Summary Form

[Genetic Testing Consent Form MiSBIE], and sample collection instructions remotely with these participants or at the Columbia University Irving Medical Center research site.

Sample #2

Sample subject population:

Subject Population	Number of completers required to accomplish study aims	Projected number of subjects who will be enrolled to obtain required number of completers	Age range of subject population

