SAP and Results: Given the non-Gaussian distribution of this data, we conducted the Kruskal-Wallis test to examine differences in heart rate elevation among four clinical groups.

Given the non-Gaussian distribution of this data, we conducted a Mann-Whitney U test to examine differences in heart rate elevation between the control group and combined mitochondrial disease groups (m.3243A>G, MELAS, and deletion). The Mann-Whitney U test indicated that there were no statistically significant differences in heart rate elevation among the groups ($p = 0.42$, $d = 0.27$).

4. ***Correlation between anxiety and mitochondrial respiration***

The association between mitochondrial respiration using extracellular flux analysis (Seahorse) on blood lymphocytes, and anxiety symptoms measured using the state and trait anxiety inventory (STAI), will be quantified by a linear regression across all study participants.

[Time Frame: Day 1]

SAP and Results: Mitochondrial respiration in isolated lymphocytes was measured on a XFe96 Seahorse extracellular flux analyzer. In brief, 0.25M live lymphocytes were seeded in an extracellular flux cell culture plate, and a MitoStressTest was performed following the manufacturer's protocol. Baseline oxygen consumption rate (OCR) was corrected for non-mitochondrial respiration (OCR after rotenone/antimycinA injection) to quantify basal mitochondrial respiration. Linear regression analysis across all participants revealed that higher values of mitochondrial respiration in isolated lymphocytes are associated with lower *state* anxiety ($R^2 = 0.05$, $p = 0.04$). However, the relationship between mitochondrial respiration and *trait* anxiety was not significant ($R^2 = 0.01$, $p = 0.49$).

5. ***Average neuropsychological function***

Groups will be compared on the fluency/initiation domain of executive functioning assessed using the Delis-Kaplan Executive Function System (D-KEFS) test.

[Time Frame: Day 2 neuropsychological session]

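### Secondary Outcome 4 is defined as one respiration–anxiety association but tested on both STAI scales with no adjustment; the state-anxiety result (p = 0.04) does not reach 5% once its own two tests are counted.

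*SAP*

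**What the plan says.** The definition under SAP Secondary Outcome 4 is written in the singular. It says that the link between respiration and "anxiety symptoms measured using the state and trait anxiety inventory (STAI), will be quantified by a linear regression across all study participants". The inventory is named, but neither of its scales is chosen as the test variable.

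The results paragraph of the same outcome reports two regressions:

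- State: "Linear regression analysis across all participants revealed that higher values of mitochondrial respiration in isolated lymphocytes are associated with lower *state* anxiety", with R² = 0.05 and p = 0.04.
- Trait: "However, the relationship between mitochondrial respiration and *trait* anxiety was not significant", with R² = 0.01 and p = 0.49.

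Both p-values are unadjusted. Neither document states a significance level, an order between the scales, a multiplicity rule or an exploratory label for this outcome. The Specific Aims in the protocol do not mention this association, so they do not settle which scale was meant.

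**The concern.** The outcome asks one question: is mitochondrial respiration associated with anxiety? The state scale answers yes, the trait scale answers no, and nothing written decides between them. If either scale can deliver a positive answer at the full nominal level, the error rate for the outcome as defined is above that level, and the smaller p-value overstates the evidence.

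This affects a stated conclusion. The state result is the only nominally positive one among the secondary outcomes (heart rate p = 0.42, letter fluency p = 0.61), and the SAP words it as something the analysis showed.

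**Working it through.** **Inputs.** From SAP Secondary Outcome 4: state R² = 0.05, p = 0.04; trait R² = 0.01, p = 0.49. Three inputs are assumptions:

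- *Alpha.* None is stated. Two-sided 0.05 is inferred from Primary Outcome 1, where a p-value just under 0.05 is called significant: "The AUCi showed a significant 86.8% higher level in the MitoD group compared to the Control (20.91 ng/mL vs. 11.21 ng/mL, $p = 0.049".
- *Model.* One predictor per regression, since no covariates are mentioned.
- *Correlation between the state and trait scales.* Not given. The range 0.5 to 0.8 is used, with more extreme values shown.

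**Step 1: are the reported figures plausible?** The regression n is not given, so p = 0.04 cannot be reproduced directly. It can be solved for n with t = √[R²(n − 2)/(1 − R²)] on n − 2 degrees of freedom. At n = 85, t = √(0.05 × 83/0.95) = 2.09 and p = 0.0397, which matches the SAP. Allowing for rounding of R² and p, the state result implies n of 74 to 99 and the trait result n of 34 to 99. A common n of 74 to 99 fits both, so the figures are mutually consistent. The protocol plans 30 + 30 + 100 + 30 = 190 completers, so the n behind a regression said to cover all participants needs to be printed.

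**Step 2: false-positive rate for the pair.** If independent, 1 − 0.95² = 0.0975. For correlated tests, the probability that at least one of two standard-normal statistics passes its two-sided 0.05 limit is:

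| Scale correlation | Rate | Ratio to 0.05 |
|---|---|---|
| 0 | 0.0975 | 1.95 |
| 0.5 | 0.0907 | 1.81 |
| 0.7 | 0.0835 | 1.67 |
| 0.8 | 0.0781 | 1.56 |

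**Step 3: adjusted p-values without using the correlation.** Holm: state 2 × 0.04 = 0.08; trait max(0.08, 0.49) = 0.49. Šidák for state: 1 − 0.96² = 0.078. A printed 0.04 may stand for 0.035 to 0.045, so the Holm value for state lies between 2 × 0.035 = 0.07 and 2 × 0.045 = 0.09.

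**Step 4: adjusted p-values using the correlation.** This is the probability that the larger of the two absolute statistics exceeds the observed state statistic:

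| Scale correlation | Raw p = 0.035 | Raw p = 0.04 | Raw p = 0.045 |
|---|---|---|---|
| 0.5 | 0.064 | 0.073 | 0.082 |
| 0.7 | 0.059 | 0.067 | 0.076 |
| 0.8 | 0.056 | 0.063 | 0.071 |
| 0.9 | 0.050 | 0.057 | 0.064 |
| 0.95 | 0.046 | 0.052 | 0.058 |
| 0.99 | 0.040 | 0.045 | 0.051 |

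Across 0.5 to 0.8 every entry is above 0.05. The result becomes borderline if the unrounded p is near 0.035 and the correlation is about 0.9 or more. At p = 0.04 as printed, the adjusted value is still 0.052 at a correlation of 0.95.

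**The case against.** The strongest reply is that this is a secondary outcome in an observational, mechanistic study. The inventory is named with both its parts, so testing both was foreseeable. The phrase about a linear regression can be read as naming the method rather than counting tests. Both results stand in adjacent sentences with R² and raw p-values, and the SAP says associated, not significant, for state. All of this is fair. It rules out any suggestion of concealment and limits the severity. It does not make the uncorrected claim sound: no text labels the outcome exploratory or says which scale answers the question, and the next sentence sets the state result against a trait result called not significant. Because two scales were foreseeable, a rule could have been written.

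Three stronger readings should be resisted:

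- *That the error rate is roughly doubled.* This holds only near zero correlation. At 0.5 to 0.8 the ratio is 1.6 to 1.8.
- *That state and trait relate differently to respiration*, because one p-value is below 0.05 and the other is not. The SAP does not test that difference. It cannot be determined from the reported figures, since neither the sign of the trait slope nor the correlation between the scales is given. The adjacent sentences should not be read as showing a difference, and equally the figures do not show that there is none.
- *That the state association is false.* A p-value of 0.08 after adjustment does not show that.

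**Conclusion.** The point holds for a secondary outcome and changes how its one positive statement should be worded. One association was defined, two were tested without adjustment, and the favourable one was written up as a finding. Counting its own two tests, the state result moves from p = 0.04 to 0.08 by Holm, or to 0.063 to 0.073 at scale correlations of 0.8 to 0.5. It is therefore a nominal association that does not reach 5%. The conclusion rests on an assumed two-sided 0.05 level and on the absence of a prior record naming one scale. If such a record names state, p = 0.04 stands as the single test of this outcome. If it names trait, the outcome is negative at p = 0.49.

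**What to change.** In the results paragraph of Outcome 4:

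1. Print the Holm-adjusted p-values (state 0.08, trait 0.49) beside the raw ones.
2. Give the regression n and both slopes with 95% confidence intervals.
3. Reword the state result as a nominal, exploratory association that is not significant after correction for the two scales.
4. If a record dated before the data were seen names one scale, cite it, use that scale alone as the test and label the other supportive. The SAP cannot serve as that record, because it already carries the results and its definition names no scale.
5. Word the state and trait results so that no difference between them is implied.

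The cost is a few lines of text and a short calculation on data already in hand. The downside is that the only nominally positive secondary result is no longer presented as established.

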Individuals with single large-scale mitochondrial DNA deletions	30	33 (accounting for 10% attrition or unusable data)	18 to 60

Description of subject population:

We will investigate individuals carrying a single large-scale mtDNA deletions that causes CPEO (chronic progressive ophthalmoplegia) and Kearns-Sayre syndrome (KSS) (52). [name] follows >20 patients with CPEO/KSS, and leads a national consortium (NAMDC – North American mitochondrial disease consortium) where >70 patients with CPEO/KSS have consented to be contacted for research. From this group, patients who have previously had diagnostic testing confirming the presence of mtDNA single deletion will be identified and invited to participate in the study.

Individuals without a confirmed genetic test who are otherwise eligible and who have family members with single large-scale mitochondrial DNA deletions and/or suspect they have the deletion will be invited to provide a buccal or urine sample to test for mitochondrial mutations. The genetic counselor or physician will review the specific consent form for genetic testing [Genetic Testing Consent Form MiSBIE], and sample collection instructions remotely with these participants or at the Columbia University Irving Medical Center research site.

Sample #3

Sample subject population:

Protocol Summary Form

Subject Population	Number of completers required to accomplish study aims	Projected number of subjects who will be enrolled to obtain required number of completers	Age range of subject population
Controls	100	118 (accounting for 10% attrition or unusable data n=10 and pilot testing n=8)	18 to 60

Description of subject population:

We will study healthy individuals without a diagnosis of mitochondrial disease recruited from the community. These participants will be age-, sex- and physical activity level- matched to participants from Groups 1 and 2.

Sample #4

Sample subject population:

Subject Population	Number of completers required to accomplish study aims	Projected number of subjects who will be enrolled to obtain required number of completers	Age range of subject population
Individuals with the m.3243A>G mitochondrial DNA mutation with MELAS symptoms. This is the same diagnostic group as Group 1, with the exception that patients who have experienced stroke-like episodes or seizures will not be excluded	30	33 (accounting for 10% attrition or unusable data)	18 to 60

New York State
Psychiatric Institute
Institutional Review Board
 PRISM 2022

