- (1) Recruitment: Patients with mitochondrial disease and healthy age/sex/race/physical activity level-matched controls will be recruited. As part of existing clinical care, some patients will have undergone (a) neuropsychological assessment, (b) metabolic assessment and (c) structural magnetic resonance imaging (MRI) as part of the diagnostic services of the Clinical Research Center for Muscular Dystrophy and Related Diseases Laboratory. From this patient pool, those molecularly identified to carry mtDNA defects (m.3243A>G, single deletion) will be provided with a study brochure and invited to sign a form agreeing to be contacted for future research. Potential participants will be contacted directly by the clinical coordinator or study coordinator who will provide information concerning the MiSBIE study and assess inclusion/exclusion criteria over the phone or in person. Should potential participants be interested in the study, they will be forwarded consent forms for their review.

We will screen participants for COVID symptoms at the following timepoints: during the initial screening call: the Monday night before the participant arrives, the Tuesday morning of study activities and the Wednesday morning of study activities. We will take the participant's temperature before starting study activities. We have a no-touch thermometer used for other MiSBIE procedures and have the required expertise to perform this measure.

Protocol Summary Form

[figure not shown]

Figure 1. Diagram illustrating study design and workflow.

Protocol Summary Form

For participants who agree to participate in the study, the a 2-day visit at the Columbia University Irving Medical Center will be scheduled and transportation/lodging arranged. Outside participants will be housed at the Edge Hotel (Washington Heights, [name]), and given detailed instructions to follow prior to their arrival.

(2) Initial Blood Draw and Biological Samples Collection: On the first outpatient visit (Day 1), a fasting blood draw to index allostatic load and cell isolation for mitochondrial function measurements and DNA/RNA analyses. Participants will first arrive at the Division of Behavioral Medicine, Presbyterian Hospital, 15th floor at 9:00am and will be greeted by [name], the MiSBIE study coordinator. Participants will have been instructed not to eat or drink beverages other than water starting at midnight the previous day.

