SAP and Results: To calculate a standardized score (z-score), we first adjusted raw neuropsychological scores for age using data from the reference group (control group). Predicted values from this model, representing age-adjusted scores, were used to calculate z-scores (Andrade, 2021). Next, we conducted a Mann-Whitney U test to examine differences in z-scores for D-KEFS letter fluency, a measure of fluency and initiation, between two groups: the control group and combined mitochondrial disease groups (m.3243A>G, MELAS, and deletion). The Mann-Whitney U test results indicated that there were no statistically significant differences in the fluency/initiation domain among the groups ($d = 0.11$, $p = 0.61$).

References:

Andrade, C. (2021). Z Scores, Standard Scores, and Composite Test Scores Explained. *Indian J Psychol Med*, 43(6), 555-557. <https://doi.org/10.1177/02537176211046525>

Juster, R.-P., Cipriani, E., Kerr, P., & DuBois, L. Z. (2024). Configurations, comparisons, and challenges calculating allostatic load. *Psychoneuroendocrinology*, 160, 106787. <https://doi.org/https://doi.org/10.1016/j.psyneuen.2023.106787>

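### As written, the letter-fluency z-scores are built from the age model's predicted values, which carry age and not fluency, so the reported null may not concern fluency at all

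*SAP*

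**What the plan says.** Under Secondary Outcome 5 the SAP sets the aim: "Groups will be compared on the fluency/initiation domain of executive functioning assessed using the Delis-Kaplan Executive Function System (D-KEFS) test". The scoring has two steps. First, "we first adjusted raw neuropsychological scores for age using data from the reference group (control group"). Age is the only predictor named. Second, "Predicted values from this model, representing age-adjusted scores, were used to calculate z-scores". A general article on z-scores is cited at that point. The SAP then reports: "we conducted a Mann-Whitney U test to examine differences in z-scores for D-KEFS letter fluency, a measure of fluency and initiation, between two groups", namely controls and the three mitochondrial disease groups combined. It concludes that "there were no statistically significant differences in the fluency/initiation domain among the groups", with d = 0.11 and p = 0.61.

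Neither document gives the z-score formula, the form of the age term, the SD in the denominator, a residual step or the number analysed for this outcome.

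On the design, the protocol says of controls (Description of Subject Population, Sample #3): "These participants will be age-, sex- and physical activity level- matched to participants from Groups 1 and 2". Under Study Procedures, Recruitment, it says more broadly that "healthy age/sex/race/physical activity level-matched controls will be recruited".

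**The concern.** A value predicted from age by a model fitted in controls is the score expected at that age. It is not that person's score corrected for age. The SAP nevertheless calls the predicted values themselves the age-adjusted scores and feeds them into the z-scores.

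Taken literally, no patient's own fluency score enters the comparison. Because controls are planned to be matched to patients on age, such a test would tend to be null whatever the patients' true fluency. Where matching failed, an age gap would show up as a fluency difference. Either way, the published conclusion on fluency/initiation would have no support from the test behind it.

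**Working it through.** **Can the reported result be reproduced?** No. Raw scores, ages, coefficients, residual SD and analysed n are not given. Only a consistency check is possible. By the normal approximation, p = 2[1 − Φ(d·√m)] with m = n1·n2/(n1+n2).

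- p = 0.61 gives z = 0.510, so m = (0.510/0.11)² ≈ 21.5 (19.1 to 24.3 allowing for rounding). With the Mann-Whitney efficiency of 0.955, m ≈ 22.5.
- The planned completers, 100 controls and 30 + 30 + 30 = 90 patients, give m = 9000/190 = 47.4 and p ≈ 0.45.
- An assumed 60 v 30 gives m = 20.0 and p ≈ 0.62; 68 v 31 gives p ≈ 0.61.

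The analysed sample was therefore probably smaller than planned. Secondary Outcome 4 points the same way: R² = 0.05 with p = 0.04 needs about 85 participants, since F = (0.05/0.95) × 83 = 4.37 (74 to 100 over rounding). This does not separate the two readings; it only guides the sample sizes used below.

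**Algebra of the literal reading.** Let the control model be ŷ = a + b·age.

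- A patient's ŷ contains nothing of that patient's score.
- A control's own score enters only through the fitted a and b. Mean leverage is 2/n = 2/100 = 0.02, and the largest is about 0.04.
- Standardizing ŷ is a linear rescaling, so with a linear term the z-score is a monotone function of age. The two-sided Mann-Whitney p and |d| then equal those for age itself.
- On that reading d = 0.11 is an age gap of 0.11 × 12 ≈ 1.3 years (1.1 to 1.4 for an assumed age SD of 10 to 13).

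**Simulation.** Assumptions: ages uniform 18–60, age–score correlation −0.3, linear age term, true deficit 0.5 SD, 3000 runs per setting, two-sided 5% Mann-Whitney test.

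| Ages | n | Rejects on predicted values | Rejects on (observed − predicted)/SD |
|---|---|---|---|
| Frequency-matched | 100 v 90 | 4.7% | 93.5% |
| Frequency-matched | 60 v 30 | 4.4% | 61.0% |
| Individually matched within 3 years | 100 v 90 | 0.0% | 93.1% |
| Individually matched within 3 years | 60 v 30 | 0.0% | 61.7% |

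With the correlation varied from −0.1 to −0.5 under frequency matching, predicted values stay at 4.6–5.6%. Residuals range over 91–97% (100 v 90) and 57–68% (60 v 30). The predicted-value p equalled the age p in every run.

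A second simulation (slope −0.02 SD per year, 1000 runs, 100 v 90) varied the deficit:

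| True deficit | Predicted values | Residual z |
|---|---|---|
| 0 | 4.4% | 5.3% |
| 0.5 SD | 5.2% | 92.3% |
| 1 SD | 5.5% | 100% |
| 2 SD | 5.4% | 100% |

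So even a 2 SD deficit leaves the literal test at its nominal level. With no deficit but patients 8 years older, predicted values rejected in 99.2% of runs. Residual z-scores rejected in 8.5%, somewhat above 5% because error in the control slope is carried across the age gap.

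**The case against.** The strongest reply is that this is loose wording. The passage opens by saying that raw scores were adjusted, and a z-score needs an expected value. A control-model prediction fits that role as the term to subtract. A third reading is also possible: scores moved to a common reference age, which keep each person's residual and, with a linear term, rank participants exactly as the residuals do. The SAP also cites an article for the z-score step, which was not available here and may give a formula.

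This stands as far as it goes: a faulty analysis is not demonstrated, and the reported d and p cannot tell the readings apart. But the sentence is still wrong as written, since it names the predicted values themselves as the adjusted scores, and neither benign reading matches that.

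Three smaller points also stand:

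- Age matching is a plan. Sample #3 names only Groups 1 and 2, while the tested patients include the MELAS group, and no achieved ages are reported. A null is therefore likely on the literal reading, not certain.
- The size of the simulated loss depends on an assumed deficit and assumed sample sizes. That predicted values do not respond to a deficit follows by construction.
- Back-solving sample size from d and p is rough. The same arithmetic on the heart-rate outcome (d = 0.27, p = 0.42) gives m of about 9, against about 22 here.

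**Conclusion.** The concern holds in conditional form. It is certain that the stated scoring rule does not give age-adjusted fluency scores. It is unknown whether that rule was the one run.

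If it was, d = 0.11 and p = 0.61 say nothing about fluency, and the test had roughly 5% rejection or less under age matching. A residual-based test would have had about 92–94% power at the planned size for a 0.5 SD deficit, and about 60% at the smaller sizes that the reported figures suggest. If residuals were used, the result can stand and only the sentence is wrong.

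The identity with a test on age assumes that age is the only predictor and enters linearly; the first fits the text and the second is not stated. The consequence is confined to one secondary outcome. It should be fixed, because the published conclusion depends on the answer.

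**What to change.** 1. Write the formula into the SAP: z = (observed letter-fluency score − score predicted at that age by the control model) / residual SD of the control model. State the form of the age term and the number analysed in each group.
2. Confirm from the analysis code which quantity was standardized. As a quick check, run a Mann-Whitney test on age in the same two groups. With a linear term, p = 0.61 and |d| = 0.11 on age would show that predicted values were used. A mismatch would not clear the analysis if the age term was nonlinear, so the code is the decisive source.
3. If predicted values were standardized, re-run on the residual z-scores and restate d, p and the conclusion. If residuals were used, correct the sentence only.

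A regression of raw score on group and age is a reasonable alternative, with simulated power of 94.3% (100 v 90) and 63.6% (60 v 30) for a 0.5 SD deficit under frequency matching. It is not equivalent, since it uses a pooled slope and a parametric test.

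The cost is one corrected sentence, one check, and at most one re-run on data already held.
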